**2.4 Study design**

This study will employ a single-arm, non-randomised design in which participants will act as their own control prior to undergoing 3 days of starvation. The control phase includes ~3 days of habitual energy balance assessment before coming into the laboratory for baseline metabolic and anthropometric assessment. Participants will be provided with monitoring equipment throughout the 3 days of starvation and will be asked to provide a blood sample as well as record their blood pressure, weight, and urinary ketones each day. On the middle day participants will also be asked to come into the lab to provide a blood sample at 2000 h.

**Figure 1.** Protocol schematic depicting the study design.

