## **2.6 Statistical analysis**

### *Sample estimate:*

Due to the drastic nature of the intervention outlined (i.e. the complete abstinence from energy intake), a relatively small sample size will be required. As such, based on previous research, a sample size of 6-10 participants should be sufficient to observe changes in metabolism with this duration of fast.

Descriptive statistics will be calculated using Microsoft Excel. Normality of data will be assessed using GraphPad Prism 8.0. Repeated measures ANOVA Will be employed to identify significant effects of TREATMENT & TIME for post-prandial data. Paired t-test or Wilcoxon will be used to compare variables assessed only pre-and post-intervention. One-way ANOVA will be used to assess changes in variables assessed each day. Bonferroni post-hoc tests will locate significant differences where they exist. Normalised confidence intervals will be calculated to plot as error bars on figures. The magnitude of these CIs directly infers the difference between means at each time point (i.e. statistical significance) rather than variance of individual values around the mean.

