### 5. Intervention

Participants will be provided with their last meal at ~1900 h on the day of the meal testing. From this point onwards, participants will be asked to refrain from eating for ~82 hours until their return visit to the laboratory. Throughout this period of extended fasting participants will be provided with 80 mmol sodium and 40mmol potassium daily (to consume in the form of slow-release tablets) to minimize the confounding effects of fluid deprivation and intravascular volume depletion on cardiovascular reflexes and sympathetic nervous system activity. Subjects will also be permitted to consume water, non-sugared carbonated drinks

and, with the exception of the day of the pre/post measurements, non-sugared decaffeinated coffee and tea (if they normally consume tea and coffee).

Upon waking each day participants will be asked to assess their urinary ketone levels, blood pressure, and weight. Participants will be asked to repeat this in the evening at 2000 h.

Each day participants will be asked to return to the laboratory to provide a blood sample. On the second day of starvation participants will also be asked to provide a blood sample at 2000 h.

Furthermore, throughout the intervention participants will be asked to wear an actiheart monitor in order to assess physical activity levels in response to prolonged fasting.

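### Weight, blood pressure and urinary ketones are read morning and evening, but the one-factor ANOVA for daily variables has no time-of-day term and no rule for using the two readings

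*Combined protocol and SAP*

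**What the plan says.** Section 2.6 gives the daily variables one sentence, "One-way ANOVA will be used to assess changes in variables assessed each day", followed by "Bonferroni post-hoc tests will locate significant differences where they exist". It names no time-of-day term and does not say which readings enter or which pairs are compared. Repeated measures is specified only for the meal-test data: "Repeated measures ANOVA Will be employed to identify significant effects of TREATMENT & TIME for post-prandial data".

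Section 5 sets the schedule. Urinary ketones, blood pressure and weight are read on waking, and then "Participants will be asked to repeat this in the evening at 2000 h". Blood is taken once a day, with an extra 2000 h sample on the second day of the fast. Section 2.5 lists change during the fast in body mass and blood pressure, and change in ketones, glycerol and FFAs, as secondary outcomes.

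On sample size, section 2.6 says "a sample size of 6-10 participants should be sufficient to observe changes in metabolism with this duration of fast", with no effect size, SD, alpha or power.

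**The concern.** The schedule has two dimensions, day and time of day, and the planned test has one factor. The analyst must choose how to fit them together, possibly after seeing the data, and the two simplest choices both have a cost.

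- **Enter every reading as a level.** A steady difference between waking and 2000 h then contributes to the F test and to the pairwise tests, even if fasting changes nothing. With three mornings and three evenings there are 15 pairs, of which 3 × 3 = 9 set a morning against an evening.
- **Keep one reading per day.** Rhythm drops out, but so does half the information, in a study of 6 to 10 people.

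Most affected variables are secondary outcomes. Circulating amino acids, which are primary, are affected only if they are measured in the daily samples.

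**Working it through.** **The plan's own figure.** The 6-10 participants cannot be reproduced, because the plan gives nothing to calculate from. What follows uses n = 6, 8 and 10, an assumed two-sided 5% level, and effects in units of the within-person SD.

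**Timing.** Section 5 says "Participants will be provided with their last meal at ~1900 h on the day of the meal testing". Taking 0800 h for mornings (an assumption) and a return at 82 h, home readings fall at about 13, 25, 37, 49, 61, 73 and 82 h. Blood falls at about 13, 37, 49, 61 and 82 h.

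**1. Rhythm only, both readings entered as levels.** Take three waking and three 2000 h readings, no fasting effect, and an evening-morning difference of d SD. Each of the six means lies d/2 from the average. The noncentrality of the one-factor within-participant F test is therefore λ = n × 6 × (d/2)² = 1.5nd², with 5 and 5(n − 1) df.

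| n | λ, d = 0.5 | rejects | λ, d = 1 | rejects |
|---|---|---|---|---|
| 6 | 2.25 | 15% | 9 | 52% |
| 8 | 3.00 | 19% | 12 | 69% |
| 10 | 3.75 | 25% | 15 | 82% |

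Simulation of the same layout agrees to within about two points (13-24% and 52-82%). With Greenhouse-Geisser, the simulated rates are about 5-15% at 0.5 SD and 29-72% at 1 SD.

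The full seven-reading home schedule gives a similar picture at 1 SD: 55% (n = 6) and 84% (n = 10), or 30% and 73% corrected. Blood, with its single evening sample, gives 31% and 54%, or 17% and 43% corrected.

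**2. One reading per day.** Assume a linear change of 1.5 SD over the six readings in time order, in steps of 0.3. The waking means are 0, 0.6 and 1.2, with sum of squares about their mean 2 × 0.6² = 0.72. For waking readings alone, λ = 0.72n. Using both readings halves the error variance of each day mean, so λ = 1.44n. Both tests have 2 and 2(n − 1) df.

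| n | λ, waking only | power | λ, both | power |
|---|---|---|---|---|
| 6 | 4.32 | 34% | 8.64 | 61% |
| 8 | 5.76 | 47% | 11.52 | 78% |
| 10 | 7.20 | 59% (60% simulated) | 14.40 | 89% |

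**3. Would a slope over hours fasted be better?** Simulated at n = 8 with five occasions (0, 13, 37, 61, 82 h), total change 1.25, noise SD 0.8 and between-person SD of relative change 0.4. The omnibus test is uncorrected.

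| Course | Omnibus | Per-person slope |
|---|---|---|
| Linear | 71% | 79% |
| Early plateau | 74% | 74% |
| Rise and fall | 77% | 5% |
| Linear, total change 2.0 | 97% | 97% |

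With Greenhouse-Geisser the omnibus falls to 59% for the linear course at a change of 1.25, and to 94% at 2.0.

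**The case against.** The strongest reply is that the plan never says both readings enter one factor. Its wording can mean one value per day, and waking readings alone show no inflation (2-4% with Greenhouse-Geisser). That stands: the inflation is conditional. But the plan does not rule pooling out, and the one-value reading has the power cost shown in step 2. Averaging the two readings would avoid both problems on complete days, but the plan does not state it, and the return morning has no evening partner.

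A reader might go further in three ways that the documents do not support.

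- **That the omnibus test wastes power and a slope should replace it.** Without a sphericity correction, which the plan does not mention, the gain is 8 points for a steady trend and nil for an early plateau. It reverses for a rise and fall. Section 2.1 says the research is not hypothesis driven, so an omnibus test is a legitimate choice.
- **That uneven spacing undermines the analysis.** Blood samples are uneven (gaps of about 24, 12, 12 and 21 h), but home readings are about 12 h apart with a last gap of 9 h.
- **That the test is meant for independent groups.** Repeated measures is missing from this sentence, but section 2.4 says "participants will act as their own control prior to undergoing 3 days of starvation", so a within-participant test is the natural intention. It should be written down. Taken literally, the test would have about 6% power at n = 6 and 10-12% at n = 10 for a 1.5 SD linear change, if the between-person SD is also 1.5. In that form it would show little rhythm inflation: about 5% and 11% for home readings at 1 SD.

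**Conclusion.** The concern holds in a limited form. A one-factor analysis does not match twice-daily readings, and the plan leaves the choice open. Pooling risks a false fasting effect. The risk is large for a 1 SD rhythm under either form of the test. For a 0.5 SD rhythm it is modest, and with Greenhouse-Geisser at n = 6 it is absent. Using one reading a day costs roughly 27 to 31 points of power in the assumed case (61 − 34, 78 − 47, 89 − 60).

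These sizes rest on assumed rhythm, effect and SD, 0800 h mornings, and independent within-person errors. The mismatch between schedule and model rests on none of them. The choice of slope or omnibus is a trade-off, not a fault in the plan.

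**What to change.** Replace the sentence on daily variables in section 2.6 with:

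> Variables measured on several days are analysed by a within-participant (repeated-measures or mixed) model with day of fast as a factor and time of day (waking/2000 h) as a fixed term where both are measured. The day-2 2000 h blood sample is not entered as a further level of the day factor. The change from the pre-fast value to the last fasting value at the matched time of day is reported with a 95% CI.

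Two points need care. The evening reading comes about 12 h later in the fast than the waking one, so the time-of-day coefficient mixes rhythm with fasting and should not be interpreted as rhythm alone. Section 4 names only urinary ketones for the evening of the meal-test day, so for weight and blood pressure the matched change has to rest on morning values.

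A slope over hours fasted may be added as a supportive trend analysis. It needs person-specific slopes and a definition of hours fasted for the pre-fast value, which is taken before the fast begins.

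The cost is wording only: no new data and no added burden on participants.

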### 4. Trial days

3 days prior to the first experimental visit participants will visit the laboratory to be fitted with a continual glucose monitor, an actiheart activity monitor, as well as a food diary and food scales. They will be asked to record energy intake and to standardise physical activity, caffeine, and alcohol intake.

Upon finishing the 3 days of lifestyle standardisation participants will enter the laboratory for where weight, height, waist:hip circumference, sagittal-abdominal diameter, and skin-fold will be assessed prior to assessment of resting metabolic rate, blood pressure and urinary ketones. Participants will also undergo grip strength, reaction time, and sensory experience assessment. Following this, samples of skeletal muscle and adipose tissue will be collected from the *vastus lateralis* and abdominal adipose tissue respectively. An intravenous cannula will then be placed a 10 mL blood samples will be drawn before ingestion of a carbohydrate rich porridge breakfast (7.3 mg carbohydrate·kJ).

A 3-hour postprandial period follows the ingestion of breakfast with blood samples will be collected at 15, 30- and 60-minute intervals during the first, second and third hour respectively alongside hourly expired gas samples and assessment of subjective appetite and mood. Upon completion of the 3-hour post-breakfast period, participants will have completed the visit and will be provided with a standardised lunch and dinner. Participants will also be provided with urinary ketone sticks, a blood pressure monitor, a set of weighing scales, as well as an actiheart monitor.

Participants will be asked to assess urinary ketones using provided assessment sticks in the evening at 2000 h.

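### Section 2.6 uses Bonferroni for the post-ANOVA comparisons; Holm's step-down method keeps the same family-wise bound and never rejects fewer, a small efficiency gain at almost no cost

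*Combined protocol and SAP*

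**What the plan says.** Section 2.6 (Statistical analysis) sets out three kinds of test.

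- Post-prandial data: "Repeated measures ANOVA Will be employed to identify significant effects of TREATMENT & TIME for post-prandial data".
- Daily data: "One-way ANOVA will be used to assess changes in variables assessed each day".
- Variables with two measurements: "Paired t-test or Wilcoxon will be used to compare variables assessed only pre-and post-intervention".

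Multiplicity is dealt with in one sentence: "Bonferroni post-hoc tests will locate significant differences where they exist". It does not say single-step or step-down; unqualified Bonferroni is naturally read as single-step. Section 2.6 states no alpha and does not list the comparisons to be made for each variable.

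The sample size statement is "a sample size of 6-10 participants should be sufficient to observe changes in metabolism with this duration of fast", with no effect size, SD or power behind it. Section 2.1 describes the study as exploratory and not hypothesis driven.

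**The concern.** With 6 to 10 participants, each comparison has few degrees of freedom, and a stricter significance level costs a lot of power. The post-hoc tests decide at which times the meal response, part of the primary outcome in section 2.5, is said to differ before and after the fast. They also locate change in the daily series. Bonferroni holds every comparison to alpha/m, including those examined after others in the family have already been rejected. Holm relaxes the level after each rejection while keeping the same bound. If several real differences of moderate size are present, Bonferroni can leave some undetected that Holm would have found.

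**Working it through.** **The plan's own figure.** The 6 to 10 participants cannot be reproduced, because no alpha, power, effect size or SD is given. What follows compares the two methods under stated assumptions and does not check the sample size.

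**Inputs from the documents**
- n = 6, 8, 10 (section 2.6).
- Post-prandial blood times (section 4): after a pre-meal sample, "blood samples will be collected at 15, 30- and 60-minute intervals during the first, second and third hour respectively". That gives 0, 15, 30, 45, 60, 90, 120 and 180 min, so m = 8 if pre-fast is compared with post-fast at each time.

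**Assumed inputs**
- Two-sided alpha 0.05.
- Separate paired t-tests with n - 1 df, and no preliminary ANOVA F test applied.
- Correlation 0.5 between the paired differences at different times.
- Standardised paired change dz from 1.5 to 3, with 1, 4 or 6 of the 8 differences real.

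**Rules.** Bonferroni rejects where p ≤ 0.05/8 = 0.00625. Holm orders the p-values and tests the i-th smallest against 0.05/(8 - i + 1), stopping at the first failure. The thresholds run 0.05/8, 0.05/7, ..., 0.05/1. The first equals Bonferroni's and the later ones are looser. Hence Holm rejects everything that Bonferroni rejects, and the chance of at least one rejection is identical.

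**Bonferroni power by formula.** Power = P(|T| > t(1 - 0.00625/2; n - 1)), where T is noncentral t with noncentrality dz × √n. At n = 6 and dz 1.5 the noncentrality is 1.5 × √6 = 3.67 and the critical value is 4.53, giving 37%. At n = 8 and 10 the same formula gives 65% and 84%.

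**Holm by simulation** (40,000 runs per case; average power per real difference)

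| Case | n = 6 | n = 8 | n = 10 |
|---|---|---|---|
| dz 1.5, 6 of 8 real: Bonferroni | 37% | 65% | 84% |
| dz 1.5, 6 of 8 real: Holm | 45% | 76% | 92% |
| dz 1.5, 4 of 8 real: gain | about 4 points | about 6 | about 4 |
| dz 1.5, 1 of 8 real: gain | about 0 | about 0 | about 0 |
| dz 3, 6 of 8 real: gain | at most about 4 points | about 0 | about 0 |

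**Error rate.** With all 8 comparisons null, simulated family-wise error was 4.5 to 5.1% for both methods, which is 5% within simulation error. With 4 real and 4 null it was 2.2 to 2.6% for Bonferroni and 2.6 to 4.9% for Holm. The bound is shared; Holm uses more of it.

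**Pooled error term.** If the post-hoc tests borrow the ANOVA's pooled error (assuming sphericity), Bonferroni power at dz 1.5 for 8 comparisons with 7(n - 1) df is about 77/91/97%. In simulation with independent contrasts, 8(n - 1) df and 6 of 8 real, Holm adds about 7/4/2 points at dz 1.5 and at most about 2 points at dz 2. The plan does not say which error term applies.

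**The case against.** The strongest reply is that nothing here is wrong. Bonferroni controls the family-wise error, the study is exploratory, and section 2.6 itself expects a drastic effect, where the two methods converge. That stands, and it is why this is an efficiency point only. It does not remove the point: no effect size is given, so moderate effects are not excluded, and a strong intervention may make many comparisons real, which is when Holm helps most.

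Three stronger readings are tempting, and the documents do not support them.

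- *Real differences will be missed.* That needs an effect size, an SD and a count of real differences, none of which is given. Under some plausible settings the gain is nil.
- *The plan commits to every possible pair.* Sixteen post-prandial means (8 times at 2 visits) would give 16 × 15/2 = 120 pairs. Section 5 adds an evening sample, "On the second day of starvation participants will also be asked to provide a blood sample at 2000 h"; with pre-fast, days 1 to 3 and follow-up that makes 6 blood samples, hence 6 × 5/2 = 15 pairs. Nothing adopts either family, and section 2.6 speaks of differences at each time point, which points towards 8. Power lost through a large family is in any case a matter of family size and not of Bonferroni against Holm.
- *All comparisons should be confined to contrasts with pre-fast at 8 times.* That would bar within-visit comparisons, although TIME is a named effect, and day-to-day comparisons, although section 2.3 is interested in stability of fuel use. It would also not fit the hourly gas, appetite and mood measures, or the twice-daily ketone, blood pressure and weight records.

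**Conclusion.** A minor improvement, not a flaw. For comparisons after the repeated measures and one-way ANOVAs, Holm is at least as powerful as Bonferroni under the same 5% bound. The gain per real difference reaches about 8 to 11 points at dz 1.5 with 6 of 8 real and separate paired t-tests (45 - 37 = 8, 76 - 65 = 11, 92 - 84 = 8). It shrinks with fewer real differences, very large effects or a pooled error term. All sizes rest on assumed alpha, dz, correlation and number of real differences. Holm does not cure low power at n = 6 to 10, since the first rejection is no easier. Variables measured only before and after, including the muscle and adipose amino acids from the two biopsies, have a single test each and are unaffected.

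**What to change.** Replace the Bonferroni sentence in section 2.6 with:

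> Post-hoc comparisons will be adjusted by the Holm-Bonferroni step-down method within each variable, over the comparisons planned for that variable (for post-prandial data, pre-fast versus post-fast at each of that variable's own sampling times).

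The example in brackets lets hourly measures have their own, smaller family. The comparisons planned for the daily variables remain a scientific choice for the investigators and should be settled before the data are seen.

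Cost: one sentence, with no new data or participants. Holm gives no simultaneous confidence intervals that match its decisions. Section 2.6 promises none, but it does read statistical significance from the normalised intervals plotted as error bars. Add that significance is judged from the Holm-adjusted p-values and not from those bars.

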## **2.5 Outcome measures**

### *Primary*

Metabolic response to feeding before and after a prolonged fast  
Change in amino acid metabolism (i.e. BCAAs and ketoacids) in skeletal muscle, adipose tissue, and in the circulation

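### Section 2.6 treats the size of the normalised CI error bars as showing statistical significance; bar size shows precision only, and reading the bars against the means does not in general reproduce the planned Bonferroni tests

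*Combined protocol and SAP*

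**What the plan says.** The statistical text in section 2.6 sets out three formal analyses. For the meal tests: "Repeated measures ANOVA Will be employed to identify significant effects of TREATMENT & TIME for post-prandial data". For daily variables: "One-way ANOVA will be used to assess changes in variables assessed each day". For the rest: "Paired t-test or Wilcoxon will be used to compare variables assessed only pre-and post-intervention". It then says: "Bonferroni post-hoc tests will locate significant differences where they exist".

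The next two sentences concern graphics. The first is "Normalised confidence intervals will be calculated to plot as error bars on figures". The second begins "The magnitude of these CIs directly infers the difference between means at each time point (i.e. statistical significance" and ends by contrasting this with the spread of individual values around the mean.

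The section gives no confidence level for the bars, no normalisation method, no rule for reading them and no significance level.

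**The concern.** The end of the disputed sentence is right: normalising removes between-person variation, so the bars do not describe how individuals differ. The first part does not follow from that. The width of a bar says how precisely a mean, or a within-person contrast, is estimated. It says nothing about how far apart two means are.

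The sentence also puts a second criterion for significance beside the Bonferroni tests. One of the two primary outcomes in section 2.5 is "Metabolic response to feeding before and after a prolonged fast", which will naturally be shown as time-course figures with these bars. A reader who follows the sentence could call a time point different when the planned test does not, or the reverse.

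**Working it through.** **Figure in the plan.** The disputed sentence contains no number. The only figure in section 2.6 is the sample size of 6 to 10. It comes without inputs, so it cannot be reproduced, but nothing below depends on how it was reached.

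**Inputs from the document**
- n = 6 to 10 (section 2.6), with each participant as their own control (section 2.4).
- Blood-sampling times (section 4): "blood samples will be collected at 15, 30- and 60-minute intervals during the first, second and third hour respectively". That is 15, 30, 45 and 60 min, then 90 and 120, then 180: 7 samples. With the one before breakfast there are 8 times.

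**Assumptions, not in the plan**
- 95% bars and two-sided 0.05.
- A Bonferroni family of 8 pre-post comparisons, one per blood-sampling time.

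**Step 1: same bars, different gaps.** Take one time point and normalise over its two cells (before and after the fast), with no correction for the number of conditions. If s_d is the SD of the paired differences, each normalised cell has SD s_d/2, so the half-width is

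h = t(0.975, n−1) × s_d / (2√n).

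The standard error of the mean difference is s_d/√n = 2h / t(0.975, n−1). With n = 8 and h = 0.5 this is 1.0 / 2.365 = 0.423.

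| Gap between means | \|t\| = gap / 0.423 | Unadjusted paired p (7 df) | × 8 |
|---|---|---|---|
| 0.5 | 1.18 | 0.28 | 1 (capped) |
| 1.0 | 2.36 | 0.05 | 0.40 |
| 1.5 | 3.55 | 0.009 | 0.075 |

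The bars are the same size in every row and the conclusion changes. This part of the argument needs no particular construction: no bar width contains the gap.

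**Step 2: compare the gap with the bars instead.** These bars separate when the gap exceeds 2h = t(0.975, n−1) × s_d/√n. That is exactly the unadjusted paired t-test. Bonferroni over 8 separate paired tests needs t(1 − 0.025/8, n−1). Applying the correction for a small number of conditions multiplies the bars by √(2/1).

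| Critical \|t\| | n = 6 | n = 8 | n = 10 |
|---|---|---|---|
| Two-cell uncorrected bars, non-overlap | 2.57 | 2.36 | 2.26 |
| Two-cell corrected bars, non-overlap | 3.64 | 3.34 | 3.20 |
| Bonferroni, 8 separate paired tests | 4.53 | 3.86 | 3.55 |

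The Bonferroni threshold is 1.76, 1.63 and 1.57 times that of the uncorrected bars. In the last row of the first table the bars are clearly apart (gap 1.5 against 2h = 1.0), yet the adjusted p is 0.075.

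**Step 3: look for constructions that do agree.** Build the bars from one pooled error term over all 16 cells (2 visits × 8 times), h = t(0.975, 15(n−1)) × √(MSE/n), and use the same error term in the test. The Bonferroni threshold in half-widths is

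√2 × t(1 − 0.025/8, 15(n−1)) / t(0.975, 15(n−1)).

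- n = 6: 1.414 × 2.814 / 1.992 = 2.00
- n = 8: 1.414 × 2.791 / 1.983 = 1.99
- n = 10: 1.414 × 2.778 / 1.978 = 1.99

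Non-overlap occurs at 2.00, so the two nearly coincide. If the test uses an error term on 7(n−1) df with equal error variances, the threshold stays within about 2.00 to 2.07 half-widths.

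A smaller family can also bring them together. For 4 comparisons at n = 8, Bonferroni needs |t| = 3.335, against 3.344 for two-cell corrected bars.

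**The case against.** The strongest defence is that the plan already says where significance comes from. The sentence just before the graphics text gives the job of locating differences to Bonferroni tests, and the intervals are described only as error bars. On this reading the disputed sentence merely explains why normalised intervals are preferred to SD bars, in a study that section 2.1 describes as not hypothesis driven. This stands as a limit on the harm. It does not make the sentence correct, because it explicitly equates bar magnitude with statistical significance.

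A second objection is that the bars might agree with Bonferroni after all. This stands in part. A reader might infer that 95% bars never reproduce the planned tests, and the document does not support that: it names no construction, and step 3 shows two that nearly match. The hourly measurements in section 4 (expired gas, appetite, mood) would also have a smaller family than the 8 blood samples. The defensible statement is that agreement is not general. Even where it occurs, it comes from setting the gap against the bars, not from their magnitude.

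**Conclusion.** The statement is wrong as written, whatever is assumed about level, normalisation or sample size, because significance needs the gap between means as well as the bar. The second part is conditional. For two-cell uncorrected 95% bars and 8 pre-post blood comparisons, non-overlap is an unadjusted paired t-test and falls well short of Bonferroni with separate paired tests; other constructions come close to Bonferroni.

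Two stronger readings should be resisted. A reader might infer an inflated false-positive rate for the trial, for example 1 − 0.95^8 = 0.34 for at least one of 8 time points under no effect. That figure needs independent time points and one particular kind of bar, and the plan specifies neither. A reader might also infer that the formal analysis or the sample size is undermined. Neither uses the error bars.

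The consequence is confined to conclusions read from figures, including those for a primary outcome. Severity is minor.

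**What to change.** In section 2.6:

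1. Delete the statement that the magnitude of the intervals infers a difference between means or statistical significance.
2. Keep the point that the bars do not show the spread of individual values.
3. State that the plotted normalised intervals are descriptive, and give their confidence level and normalisation method (which cells are used, and whether the correction for the number of conditions is applied).
4. State that significance is judged only from the tests already planned in that section.

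The cost is a few sentences. No new data, tests or change in sample size are needed.
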